### Analysis

Solicited AEs will be summarized by AE term for overall occurrence and by maximum intensity using frequencies and percentages. Note, only solicited events with intensity grades above 0 are considered AEs; however, subjects reporting intensity grades of 0 for the collection period will be included in summaries to account for all observed memory aid data. As intensity is still collected daily for ongoing events after day 8 of the memory aid reporting period, the maximum intensity used in summaries will be derived from the entire duration of the event and not just from the 8-day reporting period.

Summaries will be presented by cohort and vaccination arm (ABNCoV2 versus Comirnaty) for Part A, and by cohort for Part B separately using 2 different grade scales (Grading for Analyses per FDA Guidance and Grading Assessed at Dairy Review) according to Table 6 for local AEs and Table 7 for general AEs.

In addition, duration of solicited events will be summarized only for subjects experiencing the event of interest using n, mean, SD, median, Min, and Max. Although the collection period is 8 days including the day of vaccination, durations may be longer than 8 days if the solicited event is ongoing at Day 8.

Additional summaries of the subset of general AEs determined to be related to vaccination, as well as those considered both related and  $\geq$  Grade 1 and related and  $\geq$  Grade 3 using the Grading for Analysis scale per FDA Guidance, will also be presented using frequencies and percentages.

The solicited AE information from the memory aid as well as the physician’s assessments and durations will be included in subject-level listings.

Figures will be presented for all solicited local and general AEs overall and for the subset of  $\geq$  Grade 3 (based on Grading for Analysis scale per FDA Guidance) solicited AEs by cohort (Parts A and B) and vaccination arm within cohort (Part A only).

#### 4.5.2.6. Unsolicited Adverse Events

Unsolicited AEs will be assessed and documented from ICF signature through EAP, and if ongoing at that time followed until resolution or until the subject’s last trial visit, at the latest. SAEs, AESIs, and MAAEs will be collected through the end of the trial, including during the FU phase, and followed-up until resolution or achievement of stable clinical conditions.

Unsolicited AEs are graded based on the *Toxicity Grading Scale for Healthy Adult and Adolescent Volunteers Enrolled in Preventive Vaccine Clinical Trials*. The maximum toxicity grade over the duration of the AE will be reported in the eCRF. If a subject has multiple AEs

within the same PT, the highest toxicity grade will be used for subject-level summaries. Grading will be based on the descriptions listed in [Table 8](#).

**Table 8: Adverse Event Grading**

Grade	Definition
Grade 1	An AE which is easily tolerated by the subject, causing minimal discomfort and not interfering with daily activities.
Grade 2	An AE which is sufficiently discomforting to interfere with daily activities, but does not require medical intervention (non-narcotic pain reliever or other nonprescription medication are not considered “medical intervention” for this purpose).
Grade 3	An AE which prevents daily activities and which requires medical intervention (non-narcotic pain reliever or other nonprescription medication are not considered “medical intervention” for this purpose)
Grade 4	Life-threatening, or disabling.

### Analysis

In general, AEs will be summarized separately by trial part for the Safety Analysis Set in each phase (the Entire Trial Phase, Active Trial Phase, and Follow-up Phase). Within each part, cohort, and vaccination arm (Part A only), AEs will be further presented by SOC and PT. AEs occurring between ICF signature and trial vaccination will be considered Baseline Signs and Symptoms and will be reported in a similar fashion to medical history events.

Summary tables for all AEs by SOC and PT will be presented including subject and event counts, as well as percentages of subjects for the Active Trial Phase:

- AEs
- Related AEs
- AEs  $\geq$  Grade 3
- Related AEs  $\geq$  Grade 3
  - Related AEs  $\geq$  Grade 3 Occurring within 8 Days of Trial Vaccination
- SAEs
- Related SAEs
  - Related SAEs Occurring within 8 Days of Trial Vaccination
- AESIs
  - Related AESIs
- MAAEs
  - Related MAAEs
- AEs Leading to Discontinuation of the Active Trial Phase
- Non-serious AEs in  $> 5\%$  of Subjects

In addition, a combined summary of AEs will be presented for related SAEs, related unsolicited AESIs, related  $\geq$  Grade 3 AEs, and AEs leading to discontinuation within 8 days after vaccination. Grading for analysis per FDA guidance will be used for all combined summaries including solicited AEs.

An overall combined summary of solicited and unsolicited AEs including subject counts, event counts, and percentages of subjects experiencing the AE will be created for the following event categories:

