4.3 Safety Objectives

There are two safety objectives. The first is to compare, in the randomized, double-blind setting (Part A), the safety and tolerability of ABNCoV2 to Comirnaty. The second is to assess the same safety and tolerability endpoints among all subjects who receive ABNCoV2 (Parts A and B).

ABNCoV2 Clinical Trial Protocol ABNCoV2-03 Edition 8.0

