5.3 Safety Endpoints

Safety endpoints will be summarized in Part A for all subjects receiving ABNCoV2 compared to those receiving Comirnaty and in both parts for all subjects receiving ABNCoV2. The endpoints include the frequency and percentage of subjects who report the following:

- SAEs or adverse events of special interest (AESIs) assessed as related to trial vaccine during the entire trial period, which includes both the active trial phase and follow-up.
- Grade 3 or higher adverse events (AEs) assessed as related to trial vaccine in the 8-day period starting with the day of vaccination.
- SAEs, AESIs, or medically attended AEs (MAAEs), regardless of relationship, during the active trial phase.
- SAEs, AESIs, or MAAEs, regardless of relationship, during the entire trial period.
- Grade 3 or higher AEs assessed as related to trial vaccine during the active trial phase.
- Solicited local AEs in the 8-day period starting with the day of vaccination.
- Solicited general AEs in the 8-day period starting with the day of vaccination.

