6.3 Inclusion of Older Subjects

Sites will be instructed to pursue a target of 25% of enrollment to be subjects that are \geq 65 years of age for Part A and 33% to be \geq 65 years of age for Part B. The end goal is to have at least 1000 subjects \geq 65 years of age who receive ABNCoV2.

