
Part A: To assess the safety and tolerability of the ABNCoV2 vaccine compared to Comirnaty in previously vaccinated adult subjects in Part A (both cohorts).
 
Parts A and B: To assess the safety and tolerability of the ABNCoV2 vaccine in previously vaccinated adult subjects (all subjects receiving ABNCoV2).
	
Part A: For all subjects receiving ABNCoV2 compared to those receiving Comirnaty, the percent who report the safety endpoints listed below.
 
Parts A and B: For all subjects receiving ABNCoV2, the percent who report the safety endpoints listed below.
 
 
• Serious adverse events (SAEs) or adverse events of special interest (AESIs) assessed as related to trial vaccine during the entire trial phase, which includes both the active trial phase and follow-up.
 
• Grade 3 or higher adverse events (AEs) assessed as related to trial vaccine in the 8-day period starting with the day of vaccination.
 
• SAEs, AESIs, or medically attended AEs (MAAEs), regardless of relationship, during the active trial phase.
 
• SAEs, AESIs, or MAAEs, regardless of relationship, during the entire trial phase.
 
• Grade 3 or higher AEs assessed as related to trial vaccine during the active trial phase.
 
• Solicited local AEs in the 8-day period starting with the day of vaccination.
 
• Solicited general AEs in the 8-day period starting with the day of vaccination.
 

Exploratory Objectives	

To compare total binding immunoglobulin G (IgG) antibodies against the SARS-CoV-2 index virus after vaccination with ABNCoV2 or Comirnaty in subsets of each Part A cohort.
	
GMT of total binding IgG antibodies against the SARS-CoV-2 index virus at 2 weeks after trial vaccination in subsets of each Part A cohort.
 
Geometric mean fold increases, from baseline to post-baseline time points after trial vaccination, in total binding IgG antibodies

Objectives	Endpoints
	against the SARS-CoV-2 index virus in subsets of each Part A cohort.

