## 4. STATISTICAL ANALYSES

### 4.1. General Considerations

All individual data entered in the electronic case report form (eCRF) will be listed as recorded in subject-level data listings. Listings will be sorted by trial part (A or B), Cohort (1 or 2), vaccination arm (for Part A), subject, time point, and parameter (if applicable), based on the domain presented. Tables and figures for Part A will be created separately from Part B tables.

Descriptive statistics presented for categorical variables will include frequencies and percentages (i.e., n (%)), with the denominator for the percentage calculation defined in the table. Unless otherwise stated, descriptive statistics presented for continuous variables will be n, mean, median, standard deviation, minimum, and maximum.

In general, all tables and figures will be presented by cohort (Cohort 1, Cohort 2, Cohort 1+2). For Part A, tables will also be presented by vaccination arm (ABNCoV2 versus Comirnaty) within each cohort. For subject population summaries including disposition and demographics, an “Overall” column will be presented for the combined Cohort 1+2 grouping.

Unsolicited AEs will be summarized at both the event and subject level, with percentages based on subject counts. As solicited AEs can only be experienced once per event type per subject, only subject level counts and percentages will be presented.

All statistical summaries and analyses will be performed using SAS® version 9.4 or higher (SAS Institute, Cary, NC, USA).

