### **4.5. Safety Analyses**

#### **4.5.1. Extent of Exposure**

Exposure to trial vaccine will be presented as the number of subjects receiving the trial vaccine within trial part, cohort, and vaccination arm (for Part A). The number and percentage of subjects

returning memory aids for the Safety Analysis Set will also be presented. All exposure and diary data will be listed.

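### Does the SAP need its own Part A + Part B table for the safety objective that covers all ABNCoV2 recipients?

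*SAP*

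**What the plan says.** Protocol 4.3 sets two safety objectives. The first is the randomised comparison in Part A. Of the other it says: "The second is to assess the same safety and tolerability endpoints among all subjects who receive ABNCoV2 (Parts A and B". SAP Table 1 gives the matching measure under Parts A and B: "For all subjects receiving ABNCoV2, the percent who report the safety endpoints listed below". Seven endpoints follow, built from SAEs, AESIs, MAAEs, related events of Grade 3 or higher, and solicited events. Protocol 5.3 words the same point slightly differently: "in both parts for all subjects receiving ABNCoV2".

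The rules for outputs are organised by part:

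- SAP 4.1: "Tables and figures for Part A will be created separately from Part B tables".
- SAP 4.5.2.5, solicited events: by cohort and arm for Part A, and "by cohort for Part B separately using 2 different grade scales".
- SAP 4.5.2.6, unsolicited events: "In general, AEs will be summarized separately by trial part for the Safety Analysis Set in each phase".

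The summaries called combined in SAP 4.5.2.6 join solicited with unsolicited events, or several event categories. They do not join the parts. SAP 1 (Introduction) places table, figure and listing specifications in a separate document. SAP 4.8, which lists departures from the protocol, does not mention this summary.

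**The concern.** An objective normally leads to a named output. Here the objective and its percentage are stated for one group, all ABNCoV2 recipients, while each adverse-event rule stops at the boundary between the parts. The sample-size text in SAP 5.2 also counts recipients across parts (2500 + 500 = 3000). A programmer who followed only the analysis sections would produce two sets of tables, and neither would show the percentage and denominator that Table 1 promises. The pooled figure might then be missing from the report, or be added later without a stated denominator or date.

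**Working it through.** **1. Is the summary defined?** A pooled percentage needs four things, and the SAP states all of them.

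- Population: all ABNCoV2 recipients (Table 1), within a Safety Analysis Set that spans both parts (Table 3) and is summarised by vaccine actually received (SAP 3).
- Statistic: percentage of subjects reporting (Table 1).
- Endpoints and windows: the seven items in Table 1, with phases defined in SAP 4.1.5.
- Grading: the FDA scale is primary for measured solicited events (SAP 4.5.2.5).

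What the text omits is the instruction to print the column.

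**2. Can it be obtained from what is printed?** SAP 4.1 provides a Cohort 1+2 column within each part, and Part A is also split by arm. SAP 4.5.1 gives the denominators: "the number of subjects receiving the trial vaccine within trial part, cohort, and vaccination arm (for Part A", which also covers Part B. For any endpoint row, let x be the number of subjects with the event and n the number exposed to ABNCoV2:

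- pooled percentage = 100 × (x_A + x_B) / (n_A + n_B)

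The parts recruit in different countries (Belgium and Denmark; the United States), so no recipient should be counted twice.

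**3. How far would the pooled figure sit from the printed ones?** It is a weighted mean of the two part percentages, with Part A's weight w = n_A / (n_A + n_B). Hence pooled − Part B = w × (Part A − Part B).

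- SAP example: 500 / (500 + 2500) = 0.167.
- Cohort 1 of Part A was under-enrolled (SAP 2.1) and no count is given, so I assume 200 to 500 recipients from Part A. The lower end is half of the 400-evaluable minimum in Cohort 2, with none from Cohort 1. I assume 2500 to 3000 from Part B. The smallest weight is 200 / (200 + 3000) = 0.0625 and the largest is 0.167.

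If an event differed by 10 percentage points between the parts, the pooled figure would lie 0.6 to 1.7 points from Part B's.

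**4. Does the split affect detection?** First the plan's own figure: P(at least one event) = 1 − (1 − p)^n. With p = 0.001 and n = 3000 this is 1 − 0.999^3000 = 0.9503, which matches the stated 95%. Now by part, in the same example:

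- Part B: 1 − 0.999^2500 = 0.918.
- Part A ABNCoV2 arms: 1 − 0.999^500 = 0.394.
- At least one event in either set of tables: 1 − (0.0820 × 0.6064) = 0.9503.

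An event seen in either part has been seen. The lower single-part figures are not a loss caused by separate tables.

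**The case for a change.** The best case for a change is that the protocol separates two objectives and the SAP supplies an output for only one. SAP 4.8 does not list dropping the other, so the silence looks like an oversight. The primary analysis is timed within each part (SAP Table 2 and 4.7), so the date for pooled figures is also unstated. Writing it down would cost one column and a few sentences.

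The description of the text stands: no analysis section says where or when the cross-part percentages appear. The row-sorting rule at the end of SAP 4.5.2.6, which mentions Parts A and B together, is also ambiguous.

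The rest is weaker.

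- Silence in 4.8 means that the Table 1 summary is still planned.
- The rule in 4.5.2.6 is expressly a general one. The rule in 4.1 keeps Part A and Part B tables apart without excluding others. Protocol 5.3 can be read as satisfied by reporting within each part, and Protocol 12.9 describes no pooled table either.
- The timing resolves itself. The 8-day and active-phase endpoints can be joined once both parts have had their primary analysis, and the entire-trial endpoints at the final analysis.
- The by-part rules for laboratory values, vital signs, PCR and time to infection add nothing, because those tables report none of the seven endpoints.
- The age target in Protocol 6.3 ("The end goal is to have at least 1000 subjects" aged 65 or over) does not settle the matter. Part B at its maximum gives 33% × 3000 = 990, but the synopsis asks for approximately 1000, and a recruitment target is not an output rule.

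Separate tables also have a merit of their own. Part A is blinded and Part B open-label, in different countries, so a pooled percentage mixes two reporting settings and could not replace the by-part columns.

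**Conclusion.** No change is needed. This is missing detail about layout for a summary that the SAP already names, and an analyst would fill it in one sensible way: add the two ABNCoV2 counts and the two denominators. By-part counts, percentages and safety conclusions remain sound as planned. No hypothesis test or error rate is involved, and the 0.9503 detection probability is the same with or without a pooled table.

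This rests on three points: subject counts and exposure are printed by part as the SAP says; no recipient is enrolled in both parts; and Table 1 remains in force, since nothing in SAP 4.8 withdraws it. The table specifications were not available. If they already hold the column, even the layout question disappears. If they do not, the figure is still a simple sum of reported counts.

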#### Solicited and Unsolicited AEs

- All AEs
- SAEs
- AEs  $\geq$  Grade 3 (using Grading for Analysis per FDA Guidance for solicited AEs)
- AESIs
- MAAEs
- Related AEs
- Related SAEs
- Related AEs  $\geq$  Grade 3
- AEs Leading to Withdrawal from Trial

#### Solicited AEs

- Local AEs
  - AEs  $\geq$  Grade 3 Within 8 Days of Vaccination
  - SAEs
- General AEs
  - SAEs
  - AEs  $\geq$  Grade 3
  - Related AEs
  - Related AEs within 8 Days of Vaccination
  - Related AEs  $\geq$  Grade 3
  - Related AEs  $\geq$  Grade 3 within 8 Days of Vaccination
  - AEs Leading to Deferral or Discontinuation of Vaccine

#### Unsolicited AEs

- All AEs
  - SAEs
  - Related AEs

- AESIs
- AEs  $\geq$  Grade 3
- AEs  $\geq$  Grade 3 within 8 Days of Vaccination
- Related SAEs
- Related AESIs
- Related AEs  $\geq$  Grade 3
- Related AEs  $\geq$  Grade 3 within 8 Days of Vaccination
- MAAEs
- AEs Leading to Withdrawal from Trial
- Fatal AEs
- SAEs
  - Within 8 Days of Vaccination
  - Related SAEs
  - Fatal
- AESIs
  - Within 8 Days of Vaccination
  - Related AESIs
- Related AEs  $\geq$  Grade 3
  - Within 8 Days of Vaccination

Tables summarized by SOC and PT will be sorted in order of descending incidence of SOCs in the ABNCoV2 column under the combined Cohorts 1+2 column for Parts A and B, and descending order of incidence of PTs within the SOCs. For subject level frequencies and percentages, subjects experiencing an event more than once will be counted only once within SOC and PT; however, all events will be counted in the event column.

All AEs will be listed by trial part, cohort, vaccination (Part A only), subject, onset date, SOC, and PT. Separate listings will be created for SAEs, AESIs, AEs  $\geq$  Grade 3, AEs leading to discontinuation of the Active Trial Phase, and fatal AEs. Listings will include all AEs regardless of trial phase. Both grading scales for the solicited AEs will be listed.

#### **4.5.3. Laboratory**

A list of laboratory parameters collected is included in Section 11.11 of the Clinical Trial Protocol. For the purpose of analysis, laboratory data will be converted to standard Système International d'Unités (SI) units during creation of the SDTM datasets. The original laboratory values and units will also be stored in the SDTM datasets. Only the SI units will be used in tables and listings. SI units and conversions will be included in the SDTM documentation.

All measured laboratory values will be listed and summarized at each scheduled visit using descriptive statistics. Laboratory values out of normal range will be flagged as either “L” for below normal range or “H” for above normal range in listings. Clinically significant abnormal laboratory values are recorded as AEs and summarized along with the unsolicited AEs.

Toxicity will be graded based on the *Toxicity Grading Scale for Healthy Adult and Adolescent Volunteers Enrolled in Preventive Vaccine Clinical Trials*. Grade 1 or Grade 2 toxicity is only graded according to this scale if the value is outside of the institutional normal range applicable for this trial.

All laboratory tables will be presented by each trial part separately and within each part, by cohort and vaccination arm for Part A and by cohort for Part B.

Shift tables will be used to evaluate categorical changes in toxicity levels from baseline to each scheduled time point, as well as to worst toxicity grade during the Active Trial Phase, for laboratory parameters graded per the above toxicity scale.

For laboratory parameters not graded per the above toxicity scale, similar shift tables will be created based on the laboratory provided normal ranges (Low, Normal, High). Summary tables will be produced for the number of high and low laboratory values at each scheduled time point by laboratory category and parameter.

All laboratory results will be listed. Pregnancy test results will only be included in listings.

#### 4.5.4. Vital Signs

Vital signs will be graded as described in [Table 9](#) below, per the *Guidance for Industry: Toxicity Grading Scale for Healthy Adult and Adolescent Volunteers Enrolled in Preventive Vaccine Clinical Trials*. Summaries will focus on subject level changes using shifts from baseline in toxicity grade or normal range indicator. Summaries will be performed within trial part (A or B), cohort (Cohort 1, Cohort 2, and Cohort 1+2), and by vaccination arm for Part A.

**Table 9: Vital Signs Grading**

Vital Signs	Units	Mild (Grade 1)	Moderate (Grade 2)	Severe (Grade 3)	Life Threatening (Grade 4)
Fever	(°C)	38.0 – 38.4	38.5 – 38.9	39.0 – 40.0	> 40.0
	(°F)	100.4 – 101.1	101.2 – 102.0	102.1 – 104.0	> 104.0
Tachycardia	beats per minute	101 – 115	116 – 130	> 130	ER visit or hospitalization for arrhythmia
Bradycardia	beats per minute	50 – 54	45 – 49	< 45	ER visit or hospitalization for arrhythmia
Hypertension (systolic)	mm Hg	141 – 150	151 – 155	> 155	ER visit or hospitalization for malignant

					hypertension
Hypertension (diastolic)	mm Hg	91 – 95	96 – 100	> 100	ER visit or hospitalization for malignant hypertension
Hypotension (systolic)	mm Hg	85 – 89	80 – 84	< 80	ER visit or hospitalization for hypotensive shock

ER = emergency room; mm Hg = millimeters of mercury.

Note, the Grade 4 categories requiring a corresponding emergency room visit or hospitalization will not be included in this analysis, as they should be reported separately as SAEs. The frequency and percentage of subjects experiencing Fever, Tachycardia, Bradycardia, Hypertension (systolic and diastolic), and Hypotension (systolic) will be summarized for the Active Trial Phase for any occurrence and by grade within vaccination arm (part A), cohort, and trial part.

#### 4.5.5. Electrocardiograms

ECGs are only required to be performed at screening to confirm the subject is eligible for the trial. Post-vaccination ECGs are performed only if clinically indicated; therefore, results from ECGs will be included only in subject level listings.

#### 4.5.6. Other Safety Endpoints

##### 4.5.6.1. SARS-CoV-2 Infection Results via PCR

The frequency and percentage of subjects testing positive for COVID-19 infection via PCR test by visit any time after trial vaccination will be summarized by vaccination arm for each of the cohorts in Part A. For Part B, proportions will be summarized for each cohort by timepoint and overall. As collection may occur during unscheduled visits, frequencies and percentages will include all subjects who tested positive between the prior visit through the summarized visit. PCR testing and results will also be listed.

